To identify individuals who would benefit most from the intervention, a patient is defined as being non-adherent if they (1) have been less than 80% adherent to the specific class of medications used to treat the condition(s) for which they were being identified as being poorly controlled and (2) if their “average of averages” PDC for all eligible study drugs is less than 80%. For example, patients with poorly

controlled diabetes who are non-adherent to their diabetes medications but adherent to their statins and antihypertensives, would only be eligible if their average adherence across all 3 conditions is less than 80%. Patients are excluded if, prior to randomization, they have less than 6 months of continuous enrollment in the health plan (to allow adequate assessment of eligibility), are < 18 or > 85 years of age, or have no available telephone contact information, which would preclude contact for enrollment and delivery of the intervention.

Study procedures

Once identified, PCPs of potentially eligible intervention group patients will be sent a secure message using the electronic health record to ask permission to include their patient(s) in the study. If a physician does not explicitly respond to approve or disapprove of the identified patient(s) to participate in the study within 5 days, they are sent a reminder message; one day later, their patients will automatically be opted in to the study.

Patients approved for enrollment in the study are sent a letter informing them about the study along with a simple, one compartment per day, pillbox that allows for the storage of one week of medication. Patients are then contacted by telephone to schedule a phone consultation with the clinical pharmacist. At this time, they are also administered the Patient Activation Measure (PAM), a questionnaire to assess the knowledge, skills, and confidence to manage one's health and health care. The PAM is subsequently used to tailor the intervention for that individual patient.

Intervention

The central component of the multi-faceted intervention is an individually-tailored telephone consultation conducted by a clinical pharmacist who is part of the Harvard Vanguard care team. The

clinical pharmacists work at multiple sites; in order to reduce the chances of contamination, they are restricted to providing clinical services only at other intervention sites during the time period of this study.

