All intervention patients who do not opt out of trial participation are mailed progress reports at 6 months and 9 months after randomization on behalf of their PCP. These progress reports provide personalized and updated information about disease control generated using data from the electronic health record. For patients whose administrative claims data are believed by the clinical pharmacist to be an accurate representation of actual filling behavior (e.g., for patients who only use their prescription insurance plan to pay for their prescriptions), the progress reports will also provide patient-specific medication adherence information. For those patients deemed to be not improving on either clinical outcomes or medication adherence for 3 consecutive months, the pharmacist will conduct a telephone outreach to readdress barriers to adherence. For those patients that demonstrate improvement in both adherence and clinical outcomes, the frequency of contact will be decreased to a level appropriate to their support needs

The specific components of the intervention that are administered to each patient, including the number, frequency and length of the phone consultations that they receive, will be explicitly tracked to facilitate future reproducibility and scalability.

At the conclusion of the 12-month follow-up period, a brief survey will be administered to intervention patients who did not decline to speak to a clinical pharmacist. These surveys will assess each patient's self-reported medication adherence, activation, and perceptions of the clinical pharmacist program. The surveys will also be used to validate medication adherence collected by retail pharmacy filling data and administrative pharmacy claims. These surveys will be delivered via a paper mailing on behalf of the PCP. Within these paper surveys, patients will be given the option to complete the survey online through Qualtrics. Non-respondents will receive a second copy of the survey with a \$5 gift card as an incentive (see "12-month survey" in attachments section).

Outcomes

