In the primary analysis, the outcomes will be compared using generalized estimating equations with an identity link function and normally distributed errors to account for the clustering of subjects within practice sites. Our primary models will also adjust for the block-randomized design. If there are differences in baseline characteristics between study groups that are believed to be confounders of the intervention–outcome association, we will repeat our analyses after adjusting for these covariates.

A similar approach will be taken for the analysis of the secondary outcomes, except using logit link functions with binary errors and log link functions with Poisson errors, as appropriate for disease control and rates of healthcare utilization, respectively.

Several additional analyses will also be conducted. First, we will assess the correlation between calculated adherence based on insurer claims, self-reported adherence, and pharmacy transaction records (for patients filling prescriptions at Harvard Vanguard pharmacies). Second, we will use Markov modeling to assess the long-term impact of the intervention on cost, quality-adjusted survival, and cost-effectiveness of the intervention.

Sample size considerations

Our study should be sufficiently powered to detect small, clinically meaningful changes in the primary outcome. We powered the study to detect a 2.5% mean change in adherence between the intervention and control groups, assuming a standard deviation of 0.25 (a conservative assumption), clustering at the practice level with a design effect of 1.10, and a 15% non-differential loss to follow-up

rate. We assumed that 95% of potentially eligible intervention patients would be approved for study inclusion by their PCPs and that 50% of these patients would agree to a pharmacist consultation. With these assumptions, we estimated that we would need a total sample size of 4000 eligible patients to provide more than 80% power to detect differences in our primary study outcome of medication adherence. In other words, if those patients receiving the intervention demonstrate a 4.6% improvement in adherence, we will still have more than 80% power to detect an improvement of 2.5% in the overall sample. We also have substantial power to detect improvements in disease control, assuming a rate of controlled disease of 30% based on our pilot data.

Summary of changes to protocol

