The independent variable of interest is exposure to the pharmacist intervention. We will measure several variables to assess the degree of balance between patients and physicians randomized to intervention versus control, to adjust for chance imbalances, and to assess whether the efficacy of the intervention is modified by particular patient characteristics. Patient demographic characteristics and major comorbid conditions, as identified based on EHR data, will be included as independent variables

HVMA currently has an existing clinical pharmacy program. These clinical pharmacists already work collaboratively with the primary care physicians in the clinics to provide patient education and advice around medication management. Primary care physicians can currently refer patients to the clinical pharmacist using an electronic referral in the electronic health record.

Final analysis plan

Sample size considerations

Our study should be sufficiently powered to detect small, clinically meaningful changes in the primary outcome. We powered the study to detect a 2.5% mean change in adherence between the intervention and control groups, assuming a standard deviation of 0.25 (a conservative assumption), clustering at the practice level with a design effect of 1.10, and a 15% non-differential loss to follow-up rate. We assumed that 95% of potentially eligible intervention patients would be approved for study inclusion by their PCPs and that 50% of these patients would agree to a pharmacist consultation. With these assumptions, we estimated that we would need a total sample size of 4000 eligible patients to provide more than 80% power to detect differences in our primary study outcome of medication adherence. In other words, if those patients receiving the intervention demonstrate a 4.6% improvement in adherence, we will still have more than 80% power to detect an improvement of 2.5% in the overall sample. We also have substantial power to detect improvements in disease control, assuming a rate of controlled disease of 30% based on our pilot data.

Outcome Measures

Primary outcome - Adherence

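### With the plan's own 95% × 50% uptake and no effect in non-recipients, a 4.6-point gain in recipients gives 2.2 points overall, not 2.5

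*Combined protocol and SAP*

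**What the plan says.** The relevant text is the paragraph headed Sample size considerations, which has the same wording in the Final protocol and the Final analysis plan.

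- Target: "We powered the study to detect a 2.5% mean change in adherence between the intervention and control groups".
- Variability and clustering: "assuming a standard deviation of 0.25 (a conservative assumption") and "clustering at the practice level with a design effect of 1.10", together with 15% non-differential loss to follow-up.
- Uptake: "95% of potentially eligible intervention patients would be approved for study inclusion by their PCPs and that 50% of these patients would agree". What they agree to is the consultation with the pharmacist.
- Sample size: 4000 eligible patients in total, for more than 80% power.
- Restatement in terms of recipients: "if those patients receiving the intervention demonstrate a 4.6% improvement in adherence, we will still have more than 80% power". The overall effect named for that power is 2.5%.

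The last sentence is introduced as another way of saying what precedes it, so 4.6% in recipients is offered as the counterpart of 2.5% overall. The paragraph gives no other uptake rate, no effect in patients who do not receive the consultation, and no alpha or sidedness. The Statistical analyses section of the Final analysis plan specifies intention-to-treat among all randomized patients, so patients who are not reached count in the comparison.

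**The concern.** The second uptake rate applies to those who pass the first, so the two multiply, and fewer than half of the intervention arm receives the consultation. Under intention-to-treat the overall effect is then less than half of the effect in recipients, unless non-recipients also improve. Yet 2.5 is more than half of 4.6.

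This is the only sentence that tells a reader how much adherence must improve in the patients actually reached. Anyone judging whether the intervention could plausibly deliver the target effect, or interpreting a small or null overall result, would rely on it. If the conversion is wrong, the required effect in recipients is understated and the power associated with 4.6 points is overstated.

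**Working it through.** **Inputs.** From Sample size considerations: overall effect 2.5 points of PDC, SD 0.25, design effect 1.10, loss 15%, approval 95%, agreement 50%, total N 4000, effect in recipients 4.6 points. Allocation is taken as 1:1 for patients, following the 1:1 randomization of practices. Alpha is not stated; two-sided 0.05 is assumed, with one-sided 0.05 as the alternative. Power uses the normal approximation.

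**1. Reproduce the plan's sample size.**

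N = 2 × [2 × SD² × DE × (1.960 + 0.842)² / d²] / (1 − loss)

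With d = 0.025, SD = 0.25, DE = 1.10 and loss = 0.15, N is about 4,063. This is within 2% of 4000, so 4000 corresponds to an overall effect of 2.5 points. One-sided 0.05 gives about 3,202, which does not reproduce the plan's figure and so supports the two-sided assumption.

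**2. Convert the effect in recipients to the overall effect.**

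Overall = uptake × effect in recipients + (1 − uptake) × effect in non-recipients

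- Uptake = 0.95 × 0.50 = 0.475.
- With no effect in non-recipients: 0.475 × 4.6 = 2.185 points overall.
- Effect in recipients needed for 2.5 overall: 2.5 / 0.475 = 5.26 points.
- Uptake needed for 4.6 to give 2.5: 2.5 / 4.6 = 54.3%.
- Average effect in non-recipients needed to restore 2.5: (2.5 − 2.185) / 0.525 = 0.60 points.

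**3. Look for an innocent explanation.**

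- Rounding: with every input at its upper rounding limit, 4.65 × 0.955 × 0.505 = 2.24, still below 2.45, the lowest value that rounds to 2.5.
- Leaving out the 95% step: 0.50 × 4.6 = 2.30.
- Loss to follow-up: it is assumed non-differential, so it does not change the uptake fraction, and it is already in N.
- Relative rather than absolute percentages: the ratio is essentially unchanged, 47.5% against the implied 54.3%.

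**4. Power at the diluted effect.**

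SE = √[2 × 0.25² × 1.10 / (4000 × 0.85 / 2)] = 0.008993

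| Overall effect | N | Two-sided 0.05 | One-sided 0.05 |
|---|---|---|---|
| 2.5 points | 4000 | 79.4% | 87.2% |
| 2.185 points | 4000 | 68.1% | 78.4% |
| 2.5 points | 4076 | 80.1% | 87.7% |
| 2.185 points | 4076 | 68.9% | 79.0% |

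For example, z = 0.02185 / 0.008993 = 2.430, and 2.430 − 1.960 = 0.470 gives 68.1%. The 4076 rows use the patient number in the Final protocol's Background. Power at 2.185 points is below 80% in every case. Leaving out the 95% step and using one-sided 0.05 gives 81.9% at N = 4000, but the overall effect is then 2.3 points, still not 2.5.

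By the formula in step 1, 80% power (two-sided) at d = 0.02185 would need about 5,319 patients.

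**The case against.** The strongest reply is that the figures conflict only if patients without a consultation gain nothing, and the plan does not say that. The intervention has several parts, some of which reach patients who never speak to the pharmacist. Under Study procedures, "Patients approved for enrollment in the study are sent a letter informing them about the study along with a simple" pillbox. Under Intervention, "All intervention patients who do not opt out of trial participation are mailed progress reports at 6 months and 9 months after randomization". An average gain of 0.6 points in all non-recipients would reconcile 4.6 with 2.5. If the gain were confined to approved patients who decline the consultation, it would be 0.315 / 0.475 = 0.66 points. Either is about one-seventh of the effect in recipients, which is not implausible.

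This stands in part. The zero-effect condition belongs to this review, and every figure derived from 2.19 depends on it. But the plan assigns no adherence effect to the mailings, and if one was intended it is an undisclosed input to the power statement. The sentence still cannot be followed from the assumptions printed beside it.

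A second reply is that the power claimed is for an overall 2.5 points, which does not depend on 4.6, and that the sample size for 2.5 reproduces. The second half is correct and is accepted here. On that literal reading, however, the 4.6% clause has no function, while its conditional wording and its place as a restatement show that a conversion was meant.

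A third reply is that the consequence is small and the power figures rest on an assumed alpha. Both are true: no analysis uses 4.6, and the power figures should be read with that assumption attached. The 2.19 result itself needs no alpha.

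**Conclusion.** The concern holds. On the stated uptake, and with no effect in non-recipients, 4.6 points in recipients corresponds to 2.2 points overall. The sentence therefore understates the effect required in recipients by about 0.7 points (4.6 against 5.3). The statement "we will still have more than 80% power to detect an improvement of 2.5% in the overall sample" is not supported as the counterpart of 4.6 points in recipients. Under two-sided 0.05 at N = 4000 the mismatch costs about 11 percentage points of power (79% to 68%).

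The mismatch among the 4.6%, the 2.5% and the uptake figures is certain on the printed assumptions. Which of them is at fault cannot be told from the documents. The total of 4000 for an overall 2.5 points, the intention-to-treat comparison and the primary model are unaffected. The sentence should be corrected, but the error does not threaten the design.

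**What to change.** Restate the sentence in Sample size considerations in both the Final protocol and the Final analysis plan, in one of three ways:

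- (a) replace 4.6% with 5.3%, keep 2.5% overall, and give power as about 80%;
- (b) keep 4.6%, and say that it corresponds to about 2.2% overall with about 68% power at 4000 patients; or
- (c) if 4.6% rests on a different uptake (54.3% would be needed) or on an effect in non-recipients (about 0.6 points on average would be needed), state that assumption and its basis.

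In each case state the assumed effect in non-recipients, the alpha and the sidedness. The power figures in (a) and (b) assume two-sided 0.05 and no effect in non-recipients, and should be recalculated if the sponsor used other values.

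The cost is one sentence in two places, with no change to sample size, design or primary analysis.

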This trial is being conducted at Harvard Vanguard Medical Associates (Harvard Vanguard), which is a practice of Atrius Health, a large multispecialty medical group and a Pioneer Accountable Care Organization. Harvard Vanguard employs approximately 150 primary care physicians (PCPs) who provide care for approximately 300,000 adult patients at 17 practice sites. Of these, 15 practice sites have integrated retail pharmacies, where approximately 50% of patients obtain their prescription medications. Within each site, all PCPs and their eligible patients will be randomized to the same study arm.

Study design and randomization

STIC2IT is a pragmatic, prospective, intention-to-treat, cluster-randomized controlled trial designed to test the impact of a technologically-enabled, behaviorally-targeted pharmacist intervention designed to improve medication adherence and disease control among the specific group of individuals who are most likely to benefit from this intervention – those who are non-adherent to their glucose lowering, anti-hypertensive, or statin medications and have evidence of poor disease control based on recommended clinical targets. We randomly selected 1 of the 15 Harvard Vanguard practice sites with onsite pharmacies as a pilot site for intervention refinement. The remaining 14 Harvard Vanguard practice sites were then cluster-randomized such that all PCPs and their patients in a given practice site were assigned to the same study arm. Because the practice sites differ from each other, simple cluster randomization may have resulted in imbalances in patient or provider factors that could potentially bias outcome assessment. Therefore, we categorized the practice sites based on their size (i.e., small or large, based on the number of patients receiving care at each site) and whether clinical pharmacists at the sites

offered disease management counseling directly to patients (i.e., yes or no). Within the resultant 4 blocks, practices were then randomized in a 1:1 ratio to intervention or control using a random number generator.

Subjects

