The trial's primary outcome is medication adherence assessed at 12 months after randomization. Medication adherence will be assessed using prescription claims data and measured as the mean PDC over the 12 months after randomization using the "average of averages" approach used for study eligibility. Adherence will be measured only for medications that qualified a patient for inclusion in the study and follow-up will begin at the point of randomization

Secondary outcomes

The secondary outcomes for the study include disease control and rates of healthcare utilization.

Disease control will be measured as the following two different outcomes: (1) the proportion of patients achieving good disease control for all of their eligible conditions and (2) the proportion of patients achieving good disease control for at least one of their eligible conditions. Because disease control will be evaluated using biometrics that are collected during routine care rather than at study-prescribed intervals, we will use those values that are closest to each patient's 12-month end of follow-up period up to a maximum of 15 months after randomization

Rates of healthcare utilization will also be measured using administrative claims data and will include all-cause emergency room visits, physician office visits, and hospitalizations during follow-up

Statistical analyses

We will report the means and frequencies of pre-randomization variables separately for intervention and control subjects. Comparisons of these values will be performed using t-tests and chi square tests and their non-parametric analogs, as appropriate. The outcomes will be evaluated using intention-to-treat principles among all randomized patients. In the primary analysis, the outcomes will be compared using generalized estimating equations with an identity link function and normally distributed errors to account

for the clustering of subjects within practice sites. Our primary models will also adjust for the block-randomized design. If there are differences in baseline characteristics between study groups that are believed to be confounders of the intervention–outcome association, we will repeat our analyses after adjusting for these covariates.

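### The planned baseline tests ignore site clustering, so their p-values are too small by an amount the documents do not fix, and they should not inform the choice of adjustment covariates

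*Combined protocol and SAP*

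**What the plan says.** The Final protocol (Study design and randomization) makes the practice site the unit of allocation: "The remaining 14 Harvard Vanguard practice sites were then cluster-randomized". Sites were grouped into four blocks by size and by whether site pharmacists counsel patients directly, and "practices were then randomized in a 1:1 ratio to intervention or control using a random number generator". The reason given is that sites differ and that simple cluster randomization might leave patient or provider factors unbalanced.

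Baseline is handled in the same words in the Final protocol (Analytic plan) and the Final analysis plan (Statistical analyses): "We will report the means and frequencies of pre-randomization variables separately for intervention and control subjects", followed by "Comparisons of these values will be performed using t-tests and chi square tests and their non-parametric analogs, as appropriate". Neither place mentions clustering or blocks for these comparisons.

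Outcomes are treated differently. They are analysed by generalized estimating equations "to account for the clustering of subjects within practice sites" (Final protocol, Analytic plan), with adjustment for the blocked design.

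Later in the same text comes a conditional step: "If there are differences in baseline characteristics between study groups that are believed to be confounders of the intervention–outcome association", then "we will repeat our analyses after adjusting for these covariates". No p-value or other criterion defines a difference. The Final analysis plan (Potential confounders) adds that balance will be assessed and chance imbalances adjusted for, and it mentions demographics, comorbidity, medication use and utilization.

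**The concern.** A t-test or chi-square test on patients takes its standard error from the number of patients. Here the chance element is the allocation of 14 sites. If a variable such as age or prior utilization varies between sites, the difference between arms varies more than the test allows, and its p-value is too small. The plan recognises this for outcomes and leaves it out for baseline variables.

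Two things are at stake. First, the baseline table may mark ordinary site-to-site variation as significant and make a sound randomization look doubtful. Second, the plan repeats its analyses with adjustment when baseline differences are found, and these tests are the only baseline comparison it describes. Their p-values could therefore enter a choice of covariates made after the data are seen.

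**Working it through.** **Inputs from the documents.** 14 randomized sites (Final protocol, Study design and randomization). Total of 4000 patients, difference 0.025, SD 0.25, design effect 1.10, 15% loss (Sample size considerations, in both the protocol and the analysis plan).

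**Assumptions.** Two-sided 5% level and 80% power for the calculation; the documents do not state the level. Tests at patient level. Intraclass correlations (ICCs) of baseline variables, which the documents do not give.

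**Step 1: the plan's own figure.** Per arm, n = 2(1.96 + 0.842)² × 0.25² / 0.025² = 1570, so 3140 in total. With clustering, 3140 × 1.10 = 3454. With loss, 3454 / 0.85 = 4064. This is within 2% of the stated 4000, so the inputs are being read as intended.

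**Step 2: the ICC behind the design effect.** Average site size m = 4000 / 14 = 285.7. From DE = 1 + (m − 1) × ICC, ICC = 0.10 / 284.7 = 0.00035. This applies to the adherence outcome, not to any baseline variable.

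**Step 3: actual error rate of an unadjusted test.** With no true difference, the usual test statistic has variance DE instead of 1. Its rejection rate at nominal 5% is 2 × [1 − Φ(1.96 / √DE)].

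| ICC | DE | 1.96/√DE | Actual rate |
|---|---|---|---|
| 0.00035 (from DE 1.10) | 1.10 | 1.87 | 6.2% |
| 0.001 (assumed) | 1.28 | 1.73 | 8.4% |
| 0.005 (assumed) | 2.42 | 1.26 | 20.8% |
| 0.01 (assumed) | 3.85 | 1.00 | 31.8% |
| 0.02 (assumed) | 6.69 | 0.76 | 44.9% |
| 0.05 (assumed) | 15.24 | 0.50 | 61.6% |

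**Step 4: check by simulation.** The setting was 14 sites, 7 per arm, blocks ignored, 5000 replicates. The first figure is for equal site sizes, the second for sites of 140 or 430 patients.
- ICC 0.00035: 6.0% and 6.8%.
- ICC 0.01: 31.1% and 35.0%.
- ICC 0.05: 60.7% and 64.8%.

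A t-test on the 14 site means (12 degrees of freedom) rejected 4.4% to 5.7% of the time in the same runs, so a test at the level of allocation keeps its size.

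**Step 5: blocking.** A second simulation randomized within blocks of 4, 4, 4 and 2 sites; these sizes are assumed, because the documents give none. With near-equal sites it gave 21.0%, 31.1% and 61.8% at ICCs of 0.005, 0.01 and 0.05. These match the formula, so the simulation says nothing about variables that are related to the blocking factors. For those the rates would be lower. As an illustration, if blocking removed half the between-site variance, an ICC of 0.01 would behave roughly like 0.005, or about 21%.

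**Step 6: what that means for a table.** For an illustrative 20 independent baseline variables (the documents give no count), the expected number of chance flags is 20 × 0.05 = 1.0 for a valid test. It is 20 × 0.062 = 1.2 at DE 1.10 and 20 × 0.318 = 6.4 at an ICC of 0.01.

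**The case against.** The strongest reply is about size. The documents' only clustering figure implies an error rate near 6%, which is trivial, and everything larger rests on assumed ICCs. This stands as a limit on what can be claimed. It does not settle the matter, because 1.10 was set for adherence, and the protocol's own reason for blocking is that sites differ in ways that could unbalance patient factors.

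Second, patient-level testing is inferred. That is true, but the tests are named for variables summarised over subjects, and no site-level or clustered version is mentioned.

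Third, a reader might infer that the tests select the adjustment covariates. The documents do not say so. The trigger names no significance threshold and also requires that a variable be believed to be a confounder. What remains is that no other criterion for a difference is offered.

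Fourth, adjusting for a chance imbalance is a declared and legitimate aim. An imbalance in a prognostic variable is real in the sample however it arose, and adjusting for it does not by itself make the estimate wrong. This stands. The fault is in the p-value as a statement of error and in leaving the covariates open, not in adjustment.

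Finally, the adjusted models only repeat the analysis. This also stands: the primary block-adjusted model does not depend on the baseline tests.

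**Conclusion.** The point holds in a limited form. The named tests, read as patient-level, do not match the allocation of 14 sites, and their p-values are too small whenever a variable clusters by site. Nothing elsewhere in the plan corrects this. The size is not determined by the documents: about 6% in place of 5% at the design effect stated for adherence, and about 21%, 32% or 62% if a variable's ICC were 0.005, 0.01 or 0.05, with lower rates possible for variables related to site size or pharmacist counseling.

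A reader might go further and infer that the p-values must be grossly wrong, that many false imbalances are certain, or that the primary result is compromised. The documents support none of these, because they give no baseline ICC and the primary model already accounts for site and block. The harm is confined to the baseline table, to how the randomization is judged, and possibly to the choice of covariates for the adjusted repeat analyses.

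**What to change.** In the Final protocol (Analytic plan) and the Final analysis plan (Statistical analyses), replace the sentence on baseline tests with a descriptive comparison, for example: *Baseline characteristics will be described by arm, with standardized differences and the range of site means; no hypothesis tests will be performed.*

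If tests are kept, use the site-clustered, block-adjusted model already planned for outcomes, with a small-sample method suited to 14 sites.

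In either case, state that baseline significance does not select the adjustment covariates. List those covariates in advance, chosen on prognostic grounds from the domains in Potential confounders. The list is needed because standardized differences across 14 sites show the same chance imbalance and would not by themselves settle what to adjust for.

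The cost is a sentence or two in each document, a short covariate list and a different column in the baseline table. No new data are needed and the primary analysis is unchanged. The downside is that readers lose the baseline p-values they may expect.
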